4.3 Per-protocol population

The per-protocol (PP) populations are a subset of the FAS population.

Two separate per-protocol populations will be considered:

Per-protocol population 1 (PP1) includes all patients randomized to either of the two treatment groups and having completed the study without any major protocol violation as per blinded data review meeting. Patients must have completed all the planned study visits and have been evaluated for the primary endpoint of the study at the final visit.

Per-protocol population 2 (PP2) includes all patients randomized to either of the two treatment groups and having completed the study without major protocol violations which might have an impact on the evaluation of the primary objective of the study.

4.4 Subgroup analyses

No subgroup analyses are planned.

STATISTICAL ANALYSIS PLAN

Protocol No: MEIN/14/FEB-PWV/001 (FORWARD)

Version Number: 2.0

Date of Issue: 2018-03-16

Page 14 of 22

5 STATISTICAL ANALYSES

All statistical analyses will be performed using SAS® for Windows (Version 9.3 or later). Descriptive statistics will always be given by treatment group. For baseline and basic variables, they will also be given for the entire population. Unless otherwise noted below all analyses will be based on the FAS population.

If not stated otherwise the following standard descriptive statistics will be presented:

Descriptive statistics for continuous data

Number of subjects (N), arithmetic mean, standard deviation (SD), minimum, lower quartile, median, upper quartile and maximum will be presented. Usually mean and quartiles will have 1 decimal more, SD 2 decimals more than the original values (as given with min, max); N has no decimals. These descriptive statistics will be determined for measured values and for differences to baseline.

Descriptive statistics for categorical data

Absolute frequencies (N) and relative frequencies (%) will be presented with 0 or 1 decimal, respectively. For changes from baseline, shift tables may be generated.

Inferential statistics

If not stated otherwise all statistical tests will be performed two-sided and at a type I error probability of $\alpha=0.05$. All p-values will be rounded to three decimal places. Statistical significance will be declared if the rounded p-value will be less than 0.050. If a p-value is less than 0.001 it will be reported as "<0.001." If a p-value is greater than 0.999 it will be reported as ">0.999."

All confidence intervals (CI) will be derived two-sided and at a confidence probability of $1-\alpha = 0.95$.

Listings

All patient data will be listed by patient sorted by treatment group. Identification variables will be center number, patient number and treatment. Any derived data listed will also be stored permanently and will be calculated as outlined in section 8.1 of this SAP.

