5.7 Efficacy

The efficacy evaluation of the primary endpoint will be performed in both FAS and PP Populations. The Full Analysis Set (FAS) will be the primary analysis population for the confirmatory analysis. A sensitivity analysis based on the Per-Protocol 2 (PP2) population will be performed.

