5.7.2 Secondary endpoints

All secondary efficacy variables will be analyzed based on the FAS population.

For the analysis of continuous secondary efficacy variables, the ANCOVA model with change from baseline to respective time point as a response variable and respective baseline value and treatment group as the terms in the model will be used at each time point for the parameters listed below. The LOCF method will be used for missing data imputations.

- Changes in BNP and NTproBNP values after 12, 24 and 36 weeks of treatment
- Changes in inflammation markers (hsCRP, TNF- α , sUA, and plasma fibrinogen) after 12, 24 and 36 weeks of treatment
- Changes in oxidative stress parameters [Malondialdehyde (MDA), Myeloperoxidase (MPO) Oxidized low-density lipoprotein (Ox-LDL),] after 12, 24 and 36 weeks of treatment
- Changes in lipid profile after 12, 24 and 36 weeks of treatment
- Changes in eGFR with CKD-EPI formula after 12, 24 and 36 weeks of treatment
- Changes in urine albumin excretion as evaluated by first morning urine albumin/creatinine ratio (mg/g) after 12, 24 and 36 weeks of treatment
- Pulse Wave Analysis (including modifications of PWV, arterial stiffness, central blood pressure and augmentation index) after 12, 24 and 36 weeks of treatment
- The primary parameter PWV over time (12 to 36 weeks) will be analyzed using a repeated measurement model
- Changes in endothelial activation/adhesion markers (sVCAM, sICAM, vWF, e-selectine) after 12, 24 and 36 weeks of treatment (These parameters will be evaluated in a subset of patients enrolled in selected centers only)
- Tender and swollen joint count

Logistic regression will be used to analyze the parameters below for the difference between treatment groups at each time point where the dependent variable is defined as a binary outcome (e.g. 1 if urate concentration ≤ 6 mg/dl, 0 otherwise) and treatment group and baseline urate concentration will be included as independent variables.

- Percentage of gout patients with a serum urate concentration of less than or equal to 6 mg/dl after 12, 24 and 36 weeks of treatment
- Percentage of patients above the sUA target levels at Week 12, Week 24 and Week 36 after having reached the sUA target levels at Week 2

STATISTICAL ANALYSIS PLAN

Protocol No: MEIN/14/FEB-PWV/001 (FORWARD)

Version Number: 2.0

Date of Issue: 2018-03-16

Page 19 of 22

Proportional hazards model with treatment group as covariate will be used to investigate:

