- Time to achieve sUA target levels for all patients with baseline sUA as additional covariate
- Time to achieve sUA target levels stratified for sUA levels at baseline as follows: 8.1-8.8 mg/dl, 8.9-9.6 mg/dl, 9.7-10.3 mg/dl, 10.4-11.0 mg/dl, >11 mg/dl
- Time to achieve sUA target levels for all patients and stratified for sUA levels at baseline as follows: >8 and <9 mg/dl, >9 and <10 mg/dl, ≥ 10 mg/dl will additionally be presented

In case of deviation from proportional Hazard-assumption the log-rank-test will be used instead.

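### Some 68 to 85 secondary treatment comparisons fall under a rule that declares significance at the full two-sided 0.05, with no gate, ordering, adjustment or exploratory label

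*SAP*

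**What the plan says.** Section 5 (Inferential statistics) gives a default for every test: "If not stated otherwise all statistical tests will be performed two-sided and at a type I error probability of" 0.05. It adds a decision rule: "Statistical significance will be declared if the rounded p-value will be less than 0.050".

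Section 5.7 names a single confirmatory setting, for the primary endpoint: "The Full Analysis Set (FAS) will be the primary analysis population for the confirmatory analysis".

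Section 5.7.2 gives the secondary population ("All secondary efficacy variables will be analyzed based on the FAS population") and the models. For continuous variables it is ANCOVA, with "respective baseline value and treatment group as the terms in the model will be used at each time point for the parameters listed below". A typical entry is "Changes in BNP and NTproBNP values after 12, 24 and 36 weeks of treatment". For the binary urate endpoints, "Logistic regression will be used to analyze the parameters below for the difference between treatment groups at each time point". Proportional hazards models follow for time to the urate target: overall, with one set of baseline strata, and with a second set ("Time to achieve sUA target levels for all patients and stratified for sUA levels at baseline as follows").

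The only other significance levels in the efficacy section are the 0.1 levels in section 5.7.1 for model assumptions and for treatment-by-covariate interaction. Both belong to the primary model. The SAP has no multiplicity section.

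**The concern.** The section 5 default applies unless something else is stated, and section 5.7.2 states nothing else about level, order, family or dependence on the primary result. Read literally, a difference in BNP, an oxidative stress marker, an adhesion marker or Week 12 pulse wave analysis is declared significant on the same terms as the primary endpoint, even if Week 36 PWV shows no difference.

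PWV also returns among the secondary analyses, within the pulse wave analysis entry at Weeks 12, 24 and 36 and in the repeated-measures model. A failed primary comparison could therefore be followed by a declared PWV effect at another visit. With this many tests, some declaration is probable by chance alone, and the plan gives the reader no way to separate it from a real effect.

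**Working it through.** **The plan's own figure.** The SAP gives no family-wise error rate for the secondary endpoints. Its one related figure, in section 2.4, is for the primary contrast: 79 per group, difference 1.8 m/sec, SD 3.75 m/sec, two-sided 0.05. A noncentral t calculation gives power 0.8504, which agrees with the stated 85%. The 0.05 is therefore fully used by that one comparison.

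**Step 1: count the secondary between-arm tests (section 5.7.2).** Where the SAP does not list components, the count is an assumption and is shown as a range.

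| Group | Low | High |
|---|---|---|
| BNP, NTproBNP | 2 | 2 |
| hsCRP, TNF-α, sUA, fibrinogen | 4 | 4 |
| MDA, MPO, Ox-LDL | 3 | 3 |
| Lipid profile (components not listed) | 1 | 4 |
| eGFR | 1 | 1 |
| Albumin/creatinine ratio | 1 | 1 |
| Pulse wave analysis | 3 | 4 |
| sVCAM, sICAM, vWF, e-selectine | 4 | 4 |
| Joint counts (one combined, or tender and swollen separately) | 1 | 2 |
| **Continuous parameters** | **20** | **25** |

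- ANCOVA at three visits: 20 × 3 = 60 to 25 × 3 = 75. The visits for joint counts come from the flow chart.
- Logistic regression: 2 × 3 = 6.
- Repeated-measures PWV model: 1.
- Time to urate target: 1 to 3.
- Total: 60 + 6 + 1 + 1 = 68 to 75 + 6 + 1 + 3 = 85.

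**Step 2: expected false declarations if no secondary endpoint differs.** 68 × 0.05 = 3.4 to 85 × 0.05 = 4.25. This does not depend on correlation.

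**Step 3: chance of at least one false declaration.** With independent tests it is 1 − 0.95^k:

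- k = 68: 1 − 0.95^68 = 0.969.
- k = 85: 1 − 0.95^85 = 0.987.

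The rounding rule puts the effective threshold at about 0.0495, which gives 0.968 to 0.987 and changes nothing of substance.

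**Step 4: allow for correlation.** The SAP gives no correlations, so these are assumed. The first model takes equally correlated normal statistics, each tested at |z| > 1.96:

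| Tests | corr. 0 | 0.3 | 0.5 | 0.8 |
|---|---|---|---|---|
| 25 (Week 36 ANCOVAs only) | 0.72 | 0.61 | 0.47 | 0.24 |
| 75 (all ANCOVAs, high count) | 0.98 | 0.90 | 0.71 | 0.33 |
| 84 (near the upper total) | 0.99 | 0.92 | 0.74 | 0.34 |

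The second model makes visits of the same parameter more alike than different parameters. For 25 parameters at three visits, with 0.5 between parameters, the rate is 0.70 at within-parameter correlation 0.7 and 0.63 at 0.9.

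The third model adds the two logistic endpoints (22 to 27 variables, 66 to 81 tests) and lets the correlation between different parameters weaken across visits. With 0.7 within a parameter:

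| Between parameters | Chance of at least one |
|---|---|
| 0 | 0.92 to 0.96 |
| 0.3 | 0.85 to 0.90 |
| 0.5 | 0.73 to 0.78 |
| 0.7 | 0.55 to 0.58 |
| 0.8 | 0.44 to 0.46 |

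**Step 5: remove overlapping tests.** Cutting to 17 parameters at three visits, to drop the repeated urate and PWV analyses, still gives 0.54 to 0.86 for between-parameter correlation 0 to 0.5 and within-parameter correlation 0.7 to 0.9.

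**The case against.** The strongest reply is that the plan already separates primary from secondary. It names one endpoint at one visit, plans no interim analysis, and uses the word confirmatory only for the primary endpoint, so a reader may infer that nothing else is confirmatory. The primary error rate is untouched. The declaration rule sits among rounding and display conventions and could be read as reporting style. In a Phase IV trial, unadjusted p-values for secondary biomarkers are common, and the unseen protocol may call them exploratory.

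The count can also be challenged. Several tests revisit urate or PWV, the third time-to-target item is described as an additional presentation, and the lipid, pulse wave and joint-count components are not fully specified. The calculation assumes no difference anywhere; a real urate difference would take the urate tests out of the false-positive count.

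Some of this stands. The primary inference is safe, a primary/secondary distinction exists, and 68 is a fair lower bound. What is absent is any order among the secondaries and any gate to the primary. An inference from the word confirmatory does not cancel an explicit rule that significance will be declared, and a protocol label would contradict that rule unless the SAP repeated it. Removing the overlaps lowers the rate but leaves it far above 5%.

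**Conclusion.** The concern holds. This is a stated rule with a wide reach, not a detail left to another document. Under it, 68 to 85 secondary comparisons may each be declared significant at two-sided 0.05. If no secondary endpoint differs, 3.4 to 4.25 false declarations are expected, and at least one is more likely than not unless correlation across largely unrelated markers is very strong (about 0.7 to 0.8 or higher). Even the 33% obtained for 75 tests at correlation 0.8 is more than six times 0.05.

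These rates rest on assumed correlations, assumed component counts and no true difference on any endpoint counted. The direction and order of magnitude survive every plausible variation of them. The validity of the Week 36 PWV test is not in question; what should be corrected is what may be claimed from the remaining analyses.

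**What to change.** Make two changes to the SAP before database lock.

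1. Section 5, Inferential statistics: limit the sentence on declaring significance to the primary analysis, that is, the FAS ANCOVA of Week 36 PWV.
2. Section 5.7.2, add: *All secondary analyses are exploratory. Estimates with 95% confidence intervals and nominal, unadjusted p-values are presented; no statistical significance is declared and no confirmatory claim is made, whatever the result of the primary analysis.*

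If the sponsor wants a confirmatory claim on a secondary endpoint, name a short fixed sequence at Week 36 only, tested at two-sided 0.05 and only if the primary test is significant, and label the rest exploratory. Bonferroni over the whole list would also control the error, but at 0.05/68 = 0.00074 to 0.05/85 = 0.00059 per test, which is a severe price for this many markers.

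The wording change needs no new data, patients or programming. Its cost is that an isolated secondary p-value below 0.05 can no longer be called statistically significant.

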5.1 Conventions

5.1.1 Baseline definition

Baseline is defined as the last value on or prior to randomization and before first IMP administration.

5.1.2 Missing data

The primary end point will be analyzed by two approaches, without any kind of imputation and with imputation of missing data. For the primary end point missing data will be imput-

STATISTICAL ANALYSIS PLAN Protocol No: MEIN/14/FEB-PWV/001 (FORWARD)	
Version Number: 2.0	Page 15 of 22
Date of Issue: 2018-03-16	

ed using the Last Observation Carried Forward (LOCF) approach. For the purpose of evaluating the robustness two further approaches will be performed:

- imputations based on the means of available data within a treatment group at a given time point will be conducted if feasible.
- no imputation at all will be done

For the secondary end points, missing values will also be imputed by use of the LOCF approach.

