2.4 Planned sample size

A sample size of 79 in each group will have 85% power to detect a difference in means of 1.8 m/sec at Week 36 assuming that the common standard deviation is 3.75 m/sec using a two group t-test with a 0.05 two-sided significance level. Expecting a drop-out rate of approximately 15%, the total number of subjects to be randomized in order to achieve the planned sample size will be 91 per treatment arm, in total 182.

STATISTICAL ANALYSIS PLAN

Protocol No: MEIN/14/FEB-PWV/001 (FORWARD)

Version Number: 2.0

Date of Issue: 2018-03-16

Page 12 of 22

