5.7.1 Primary endpoint

The primary efficacy endpoint is Pulse Wave Velocity (PWV) after 36 weeks of treatment with febuxostat or allopurinol.

At least two PWV measurements will be taken per visit. The evaluation of measurements will be performed by two independent laboratory teams. Values valid to be included in analysis will be selected by experienced medical experts. Details on processes related to the assessment and final selection of the PWV/PWA reports that will be used for the statistical analysis are described in the document named: “PWV/PWA reconciliation process” section 15.5 Appendix E of Data Management Plan. Mean values from all measurements considered to be valid will be calculated per visit and will result in one value per visit per parameter.

Analysis of covariance (ANCOVA) with the 36 weeks PWV value as dependent variable, treatment group as factor and age, baseline blood pressure, baseline PWV as covariates, will be used to compare the efficacy of the two treatment groups.

The assumptions of the underlying model such as normality of residuals and homogeneity of variance will be investigated using significance level of 0.1.

All covariates found not to be statistically significant at the 0.05 two-sided significance level, will be removed from the model and the final model will only include statistically significant covariates.

For covariates found to be significant, the treatment by covariate interaction will be evaluated using ANCOVA model with the terms for treatment, covariate and treatment by covariate interaction.

If interaction is statistically significant at the 0.1 two-sided significance level, additional analyses will be performed to explore the interaction.

A sensitivity analysis with the change from baseline to Week 36 as response variable will be performed similarly to the primary analysis.

The relationship between PWV at Week 36 (change from baseline to Week 36) and febuxostat as well as allopurinol dose will be explored using scatterplots.

The LOCF method will be utilized for missing data imputations as described in section 5.1.2.

STATISTICAL ANALYSIS PLAN

Protocol No: MEIN/14/FEB-PWV/001 (FORWARD)

Version Number: 2.0

Date of Issue: 2018-03-16

Page 18 of 22

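### Filling missing Week 36 PWV with the treatment-arm mean understates the standard error of a planned robustness check, and section 5.1.2 gives the unimputed analysis two roles

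*SAP*

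**What the plan says.** Section 5.1.2 opens: "The primary end point will be analyzed by two approaches, without any kind of imputation and with imputation of missing data". It then names LOCF as the imputation method. For robustness it adds two further approaches. The first is that "imputations based on the means of available data within a treatment group at a given time point will be conducted if feasible"; the second is an analysis with no imputation.

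Section 5.7.1 sets the primary model as an ANCOVA of Week 36 PWV on treatment, age, baseline blood pressure and baseline PWV. It closes: "The LOCF method will be utilized for missing data imputations as described in section 5.1.2". Section 5.7 makes the full analysis set (FAS) the confirmatory population. Section 4.2 admits to it only treated patients with at least one PWV after randomization, and the flow chart in section 2.3 puts the first such PWV at Week 12.

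Section 5.7.2 first describes a per-visit ANCOVA for the continuous secondary variables and says that LOCF is used. The list under that sentence includes this item: "The primary parameter PWV over time (12 to 36 weeks) will be analyzed using a repeated measurement model".

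Section 2.4 expects drop-out of about 15% and randomizes "91 per treatment arm, in total 182".

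**The concern.** A robustness check should be able to disagree with the main result for sound reasons. Arm-mean filling cannot do this. It adds no information about the missing patients, yet it enlarges the apparent sample and narrows the apparent spread. Without covariates its point estimate equals the observed-case estimate exactly, and only the standard error changes. A reader could take a significant mean-filled result as support when it is the observed-case result with a standard error that is too small.

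Three smaller matters go with it:

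- LOCF substitutes an earlier visit for Week 36, the time point named in the primary objective.
- The unimputed analysis appears first as one of two approaches to the primary endpoint and then as one of two further robustness approaches. Section 5.1.2 never says outright which result is confirmatory.
- If LOCF were applied before the repeated-measures model, it would fill the gaps that such a model can handle without filling.

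**Working it through.** **Inputs.** From section 2.4: 79 per arm, 85% power, difference 1.8 m/s, SD 3.75 m/s, two-sided 0.05, drop-out about 15%, 91 randomized per arm. Assumed, because the SAP gives no figures: the correlation between visits, values missing completely at random, and the time course of the effect.

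**The plan's own figure.** The noncentral t distribution gives power 0.8504 at 79 per arm, so the stated 85% reproduces.

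**Arm-mean filling, formula.** Let n be the arm size and m the missing fraction.

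- The estimate rests on (1−m)n observed values per arm, so its true SE is SD × √(2/((1−m)n)).
- Filled values add nothing to the residual sum of squares but count in the sample size. The estimated variance is therefore about (1−m)SD², and the reported SE is about SD × √((1−m) × 2/n).
- The ratio of reported to true SE is 1−m.
- The actual two-sided error is about 2 × (1 − Φ(1.96 × (1−m))).

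With n = 91 and m = 0.15, the reported SE is 3.75 × √(0.85 × 2/91) = 0.513. The true SE is 3.75 × √(2/77.35) = 0.603. The ratio is 0.85.

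This derivation has no covariates. With baseline in the model the filled patients' residuals are no longer exactly zero, so the formula was checked by simulation under no treatment effect: 91 per arm, SD 3.75, ANCOVA on baseline PWV, 10,000 trials per setting, correlation 0.5 between visits (0 to 0.7 for the 15% row).

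| Missing in analysed set | Formula | Arm-mean ANCOVA | LOCF ANCOVA | Observed-case ANCOVA |
|---|---|---|---|---|
| 5% | 0.063 | 0.066 | 0.052 | 0.051 |
| 10% | 0.078 | 0.078 | 0.049 | 0.049 |
| 15% | 0.096 | 0.099–0.103 | 0.051–0.053 | 0.051–0.054 |
| 20% | 0.117 | 0.116 | 0.050 | 0.049 |

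In a further simulation at 15% missing (correlation 0.6, 6,000 trials), only the arm-mean analysis was significant in 5.2% of null trials, and only the observed-case analysis in 0.35%. The errors run almost wholly towards false reassurance.

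**Share missing in the FAS.** If 5% of randomized patients are lost before each of Weeks 12, 24 and 36, the first 5% are not in the FAS. The share missing at Week 36 is then 10/95 = 10.5%, and the formula gives about 8%.

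**LOCF dilution.** Assume that the effect builds up linearly to 1.8 m/s, so that it is 0.6 at Week 12 and 1.2 at Week 24.

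- 5% lost before each visit: (0.85 × 1.8 + 0.05 × 1.2 + 0.05 × 0.6)/0.95 = 1.705, a dilution of 5.3%.
- 15% lost after Week 12, half carrying Week 12 and half Week 24: 1.53 + 0.075 × 0.6 + 0.075 × 1.2 = 1.665, a dilution of 7.5%.
- Extreme case, all 15% carrying Week 12: 1.53 + 0.15 × 0.6 = 1.62, a dilution of 10%.

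**LOCF with unequal drop-out.** With no treatment effect, 10% and 20% missing in the two arms and a common drift of 1.0 m/s over 36 weeks, the carried values fall short by 0.5 m/s on average. The bias is 0.10 × 0.5 = 0.05 m/s, and the simulated error was 0.047 (6,000 trials).

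**The case against.** The strongest reply is that the confirmatory result is not affected. Sections 5.1.2 and 5.7.1 both point to LOCF, section 5.7 fixes the FAS, and the other two approaches are introduced as robustness checks. The arm-mean analysis runs only where feasible. It would stand beside an unimputed analysis that is valid under random missingness, and beside a repeated-measures model. Its error reaches about 10% only if all of the 15% who drop out remain in the analysed set, which section 4.2 makes unlikely. The LOCF dilution rests on an assumed time course, runs towards no difference, and at 0.095 to 0.18 m/s is 0.17 to 0.32 of an unadjusted SE of 3.75 × √(2/91) = 0.556.

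Most of this stands, and it limits the point. It does not rescue the arm-mean check: a lower missing share makes the error smaller but does not make the method valid. The feasibility condition has no criterion, so whether the check is run is also left open.

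A reader might infer that the plan doubles the trial's false-positive rate. The SAP does not support that. The inflation belongs to one robustness check, and LOCF ANCOVA kept about 5% in these simulations. A reader might also infer that the confirmatory estimate has ceased to be a 36-week effect, or that nothing ranks the analyses. Both go too far. At the planned drop-out, about 85% or more of the values are observed at Week 36, and section 5.7.1 names LOCF for the primary analysis. The conflict over the unimputed analysis is therefore one of wording. The placing of the repeated-measures item is an ambiguity, because the LOCF sentence follows the per-visit ANCOVA and the item names its own model.

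**Conclusion.** The arm-mean check is wrong as written. Under random missingness its standard error is too small by about the missing fraction, and its nominal 5% becomes about 6%, 8% and up to about 10% at 5%, 10% and 15% missing in the analysed set. These figures assume 91 per arm and an ANCOVA adjusting for baseline PWV alone; they changed little across the correlations tried.

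The confirmatory LOCF test is not inflated in this way. LOCF can still bias the 36-week effect if the treatment difference is changing over time, or if PWV drifts and drop-out differs by arm. The SAP does not allow the size to be fixed. About 5 to 8% dilution is an illustration under linear build-up, not an estimate.

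The double role of the unimputed analysis is a real but modest conflict. The LOCF reading of the repeated-measures model needs one clarifying clause. Taken together, this should be fixed before database lock, but it does not undermine the confirmatory test.

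**What to change.** - In section 5.1.2, delete the arm-mean imputation. Replace it with multiple imputation within arm, using baseline, Week 12 and Week 24 PWV and the model covariates (age, baseline blood pressure), combined by Rubin's rules.
- State once, in the same words in sections 5.1.2 and 5.7.1, which single analysis is confirmatory. Label the observed-case ANCOVA as a sensitivity analysis.
- In section 5.7.2, say that the repeated-measures model of PWV runs on unimputed data.

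Making multiple imputation the confirmatory method and keeping LOCF as supportive would be preferable, but this depends on the protocol, which was not available here. Section 3.2 lists only the paraoxonase parameters as a deviation, so the protocol may itself specify LOCF; if it does, the change belongs in section 3.2. Wherever multiple imputation is used, the SAP also needs a rule for the steps in section 5.7.1 that drop non-significant covariates and test model assumptions, because neither has a stated form across imputed datasets. Fixing the covariate set in advance would be the simplest rule for the covariates.

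The cost is SAP wording, a little programming, and slightly larger standard errors in the robustness check. Section 3.1 has the SAP finalized before database lock and unblinding, so the change belongs before then.

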4.2 Full analysis set population

The full analysis population (FAS) includes all randomized patients who have taken at least one dose of IMP. and performed at least one primary efficacy assessment (PWV) after randomization.

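### LOCF on the binary serum urate endpoints scores FAS drop-outs last seen at target as observed responders at later visits, and no sensitivity analysis is planned

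*SAP*

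**What the plan says.** Section 5.1.2 (Missing data) gives one rule for all secondary endpoints: "For the secondary end points, missing values will also be imputed by use of the LOCF approach". The two robustness checks in that section, treatment-group mean imputation and no imputation, are attached to the primary endpoint only.

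Section 5.7.2 repeats LOCF in its paragraph on continuous variables ("The LOCF method will be used for missing data imputations"). It then lists two binary sUA endpoints, analysed by logistic regression at each time point:

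- the responder endpoint, assessed at Weeks 12, 24 and 36: "Percentage of gout patients with a serum urate concentration of less than or equal to 6 mg/dl";
- the share of patients above target at Weeks 12, 24 and 36 among those who had reached target at Week 2.

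The outcome is "defined as a binary outcome (e.g. 1 if urate concentration ≤ 6 mg/dl, 0 otherwise"; missing values are not mentioned there. On the analysis set, section 5.7.2 says "All secondary efficacy variables will be analyzed based on the FAS population". Under section 4.2, FAS members must have taken at least one dose and "performed at least one primary efficacy assessment (PWV) after randomization". The flow chart in section 2.3 schedules the first such assessment at Week 12.

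**The concern.** The responder endpoint is meant to describe urate control after a stated number of weeks of treatment. A Week 12 value carried to Week 36 is not evidence of control at Week 36, yet the logistic model gives it the same weight as a measured value. If a patient leaves because of poor tolerability while at target, that loss is recorded as a success. The companion endpoint has the same defect in the favourable direction: a drop-out last seen at target is counted as having kept it.

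The trial is open label (section 2.3), so drop-out could differ between arms. No planned analysis would show how far the responder comparison depends on carried-forward values.

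**Working it through.** **Plan's own figures.** The SAP gives no expected response rate or sample size for the sUA endpoints. Its sample size (section 2.4) concerns PWV and reproduces: 79 per arm, difference 1.8 m/sec, SD 3.75 m/sec, two-sided 0.05 gives power 0.8504, against the stated 85%. The stated 91 per arm is 79 × 1.15 = 90.85, rounded up. Only the 15% drop-out carries over to this point.

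**Inputs.**
- d, drop-out: 15% (section 2.4), stated for randomized patients.
- q, share of drop-outs at target when last seen: not in the SAP; assumed 40–80%.
- p, response rate among completers: not in the SAP; assumed where needed.

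**Rates under each rule.**
- LOCF: p(1 − d) + d·q
- Missing = non-responder: p(1 − d)
- Observed cases: p

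**LOCF against missing = non-responder.** The gap is d·q.
- q = 40%: 0.15 × 0.40 = 6 points. q = 80%: 0.15 × 0.80 = 12 points.
- These are upper figures, because they treat every drop-out as a FAS member. Patients who leave before any post-randomization PWV are outside the FAS and receive no credit.
- If half the drop-outs leave before that assessment (assumption), FAS drop-out is 0.075 / 0.925 = 8.1%. The gap is then 0.081 × 0.40 = 3.2 to 0.081 × 0.80 = 6.5 points.

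**LOCF against observed cases.** The shift is d(q − p). With d = 15% and p = 70%:
- q = 75%: 0.15 × 0.05 = +0.75 points.
- q = 40%: 0.15 × (−0.30) = −4.5 points.

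**Between-arm difference.** Against missing = non-responder, LOCF changes the difference by d_A·q_A − d_B·q_B. This is zero when drop-out and q are both equal. Two illustrations with assumed rates:

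| | Completers | Drop-out | q | LOCF | Missing = non-responder |
|---|---|---|---|---|---|
| Difference appears | 70% vs 70% | 15% vs 15% | 90% vs 30% | 73.0% vs 64.0% | 59.5% vs 59.5% |
| Difference disappears | 75% vs 65% | 10% vs 20% | 30% vs 90% | 70.5% vs 70.0% | 67.5% vs 52.0% |

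First row: 0.70 × 0.85 = 0.595, plus 0.15 × 0.90 = 0.135 or 0.15 × 0.30 = 0.045. Second row: 0.75 × 0.90 = 0.675, plus 0.10 × 0.30 = 0.030; and 0.65 × 0.80 = 0.520, plus 0.20 × 0.90 = 0.180.

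**The case against.** Several stronger readings are tempting, and the document does not support them.

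- *Everyone who stops drug while at target becomes a responder.* LOCF acts only on missing values. A patient who is off drug but still measured at Week 24 or 36 keeps the observed value.
- *LOCF inflates response rates.* That holds only against missing = non-responder. Patients last seen above target are carried forward as failures, and against observed cases the shift can be negative. Missing = non-responder is itself a choice of question, treating loss as failure, and not a known true value.
- *Unequal drop-out alone creates a difference.* Take 10% vs 20% drop-out with q and completers all at 60%: LOCF reports 60% vs 60%. A 6-point gap (54% vs 48%) appears only once drop-outs are recoded as failures. The illustrations under the working need large differences in q, and the SAP gives neither q nor drop-out by arm.
- *LOCF should go for every secondary variable.* The argument here concerns the binary sUA endpoints only; nothing above shows or sizes a problem for the continuous ones.

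It can also be said that section 5.2.1 tabulates discontinuations with reasons, so unequal loss would be visible. That is true, but it would not show the effect on the responder comparison.

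Finally, the zero-otherwise coding might be read as already counting missing as failure. It is offered as an example and is silent on missing values; read that way it would conflict with section 5.1.2. Either way the text needs settling.

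**Conclusion.** The point stands in limited form. Section 5.1.2 imputes the binary sUA endpoints by LOCF without exception, so unobserved Week 24 and Week 36 outcomes of FAS drop-outs last seen at target are analysed as observed successes, and no sensitivity analysis tests this.

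The 6–12 points per arm at the planned drop-out rest on q = 40–80%. The 3–6.5 points rest in addition on half the drop-outs leaving before the first post-randomization PWV. Both are gaps to missing = non-responder, not estimates of bias. Relative to that rule, the treatment comparison is distorted only if drop-out or q differs between arms, which is possible but not quantified in the SAP. These are secondary endpoints, so this should be changed but does not threaten the primary PWV conclusion.

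**What to change.** For the two binary sUA endpoints only:

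1. Replace LOCF in sections 5.1.2 and 5.7.2 with a stated rule: a value missing after discontinuation or withdrawal counts as not at target. For the endpoint on loss of target after Week 2, it counts as target lost.
2. Word the zero-otherwise coding in section 5.7.2 to agree with this rule.
3. Add one sensitivity analysis, on observed cases or with multiple imputation, that also covers intermittent missing values (a visit missed by a patient still in the trial).

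The cost is SAP wording, one extra derivation and one extra analysis, with no new data. Reported response rates will be lower than under LOCF, by d·q in each arm for values missing after drop-out.
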